Participants will be solicited by investigators and consented prior to participation. Once consented, participants will be scheduled for their testing session(s) per protocol procedures. If enrolled, participants will be randomized to the order of the different settings on the HVT 2.0 device in different test sessions. Each participant will present on 4 different days for testing. This is to avoid fatigue related changes in sequential tests. Additional testing sessions may be scheduled to complete data collection if needed.

Sample Size:

Because no data exist for variance around these parameters, we will plan to enroll 15 participants, each to perform 4 test sessions.

Data Safety Monitoring:

Given that this protocol is a conventional exercise test protocol and therefore very low risk and routinely performed without physician oversight, there is no plan for a Data Safety Monitoring Board. Any adverse events (AE) will be promptly reported to the IRB for consideration.

VI. Study Procedures

Screening, Enrollment, & Management

During screening, participants will be asked to participate in this study, and if so, they will provide informed consent prior to enrollment. Participants will be instructed that if at any time during the study that they wish to discontinue the study, they are free to stop the testing and discontinue study participation at any time. All study procedures will be explained to the participant prior to starting any procedures, and all participants will be given a copy of the informed consent form.

Participants will be scheduled for test sessions to complete the objectives of the study and instructed to wear exercise appropriate clothing. Participants will be informed that prior to each test session, they should abstain from caffeine or tobacco products for a minimum of 4-hours, and alcohol and strenuous exercise for 10-hours ¹⁰. Participants are instructed that if at any time during the study he/she feels faint, dizzy, short of breath, or for any reason, they should stop the test.

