Data collection during enrollment will include participant demographics (e.g., age, sex, height, weight). At each session, participant vital signs, lactate levels, dyspnea scores, work performance indices, and perception scores will be collected. The study will include four sessions, corresponding to four therapy settings being tested: (1) FiO₂=100% with Flow=5LPM, (2) FiO₂=21% with Flow=25-30LPM, (3) FiO₂=100% with Flow=25-30LPM, (4) FiO₂=21% with Flow=5LPM.

For each **test session** of the four HVT Settings, the following procedures will be followed.

Pre-Test Preparations:

Prior to starting the test, the participant will perform 2-3 second warm up sprints to acclimate to the ergometer. The cycle ergometer seating settings will be maintained consistent across all four therapy settings. Participants will be instrumented appropriately and initial data (e.g., vital signs, lactate, dyspnea) will be collected for baseline.

Wingate-type Exercise Test Procedures:

The exercise test model is called the Wingate anaerobic test. In a pre-test, the participants will Wingate test consists of pedaling with maximal effort for a series of short 8-second intervals against different loads, separated by 5 min of rest. This pre-testing is done to determine the load required for maximal power output. For the actual Wingate-type test, the participant will pedal as rapidly as possible for 60 sec against the load determined for maximal power output. Three indices of performance will be computed during the test period – peak power output, mean power output over the 60 seconds, and decrease in power (fatigue index).

At end of exercise interval, participant will be asked their perception of their level of exertion.

Recovery Interval:

Recovery interval will take place after exercise period up to 1 hour, or until participant is fully recovered and lactate levels approach baseline. A minimum of 15 samples during the recovery interval will be performed to complete lactate recovery data evaluation.

At end of recovery interval, participant perception of (1) Relief of Exertion at Recovery End, and (2) Comfort/Tolerance of Therapy will be recorded.

Sessions will be repeated on separate days, scheduled at the convenience of participant and laboratory, until a participant has completed a session at each of the HVT setting levels.

VII. Data Collection

Table 1. Key study data and collection points for each Phase of the Study.

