	Study Start	After Warm-Up	Exercise Period q60sec	Recovery Period q5min	Study End
Participant pertinent Medical History	X				
Participant Vitals * (HR, RR, SpO₂, BP)	X	X	X	X	
Lactate [La]	X	X	X	X	
Dyspnea (Borg scale)	X	X	X	X	
Perception Scores (1-10 scale)					X
Work Performance			X		

*Vitals only measured prior to start of exercise, after exercise period ends, and after recovery interval. If practical, may record real-time the HR, RR, and SpO₂ with digital sensors. This will be completed for each Therapy Settings designated in the Study Protocol.

Data collection during enrollment will include participant demographics (e.g., age, gender, height, weight). Each Therapy Settings will collect the relevant participant vitals, lactate levels, dyspnea scores, and perception scores.

Primary Endpoint

- Change in lactate over (1) the exercise test interval, and (2) the recovery interval

Secondary Endpoints

- Participant Vitals: HR, RR, SpO₂, BP
- Dyspnea Score: modified BORG score, 1-10 scale
- Exercise Test Work Performance: peak power output, mean power output over 60 seconds, and decrease in power (fatigue index)

Tertiary Endpoint

Participant Perception of Performance/Recovery [1-10 scale]

- Level of Exertion at Exercise End: "How tired do you feel?"
- Relief of Exertion at Recovery End: "How fast do you feel you recovered?"

- Comfort/Tolerance of Therapy at Therapy Segment End: "How comfortable was the therapy while you had it on during exercise? How comfortable was the therapy while you had it on during recovery?"

VIII. Statistical Analysis

Participant demographics and characteristics will be summarized, compared, and appropriate statistical testing will be performed for the continuous and categorical variables. Descriptive analyses of the primary endpoints, supporting data/variables, and secondary outcome data will be performed. Assuming a non-normal data distribution for this study, a non-parametric test (e.g., Wilcoxon Signed Rank Sum test) will be performed with significance interval of 0.05 on all applicable variables. If continuous variables present a normal distribution, between-trial comparisons will be performed using two-way (within-within; trial* post-exercise sampling times) repeated measures ANOVAs. Otherwise, for the categorical variables, the Fisher's Exact test will be performed. Further analyses may be performed on the collected data based on ongoing analyses at time of study completion to identify additional relevant results.

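### No balancing of setting order is stated and no analysis has a session term, so any drift over the four sessions stays as avoidable noise in the setting comparisons

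*Combined protocol and SAP*

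**What the plan says.** On allocation, Section V (Participant Enrollment) states that "participants will be randomized to the order of the different settings on the HVT 2.0 device in different test sessions". It mentions no block, Latin square, Williams square or other restriction. Nor does it say that the order is unrestricted. The sample size paragraph in the same section says "we will plan to enroll 15 participants, each to perform 4 test sessions", and Section VI confirms the number of periods: "The study will include four sessions, corresponding to four therapy settings being tested".

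On order effects, Section V says "Each participant will present on 4 different days for testing" and gives the reason: "This is to avoid fatigue related changes in sequential tests". Fatigue is the only order effect named. Section VI leaves the spacing open: "Sessions will be repeated on separate days, scheduled at the convenience of participant and laboratory". Preparation within a session is brief: "the participant will perform 2-3 second warm up sprints to acclimate to the ergometer". The load for the 60-second test is found in a pre-test of 8-second maximal efforts. No practice run of the 60-second test itself is described.

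On analysis, Section VIII assumes non-normal data and plans a Wilcoxon signed rank test. For normally distributed data it plans a two-way repeated measures ANOVA whose factors are given as "within-within; trial* post-exercise sampling times". Session number and sequence appear in neither.

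**The concern.** Each participant repeats an all-out 60-second test four times. Responses may change from the first session to the fourth through familiarisation or training, whichever setting is in use. Separate days address fatigue but not these effects.

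Such a drift can be handled in two places: in the design, by giving each setting the same mix of early and late sessions, and in the analysis, by a session term. The plan states neither. With 15 participants, one setting can by chance fall mostly early and another mostly late. Even when the averages are close, each person's difference between two settings still carries the drift between the two sessions, and this widens the error term. What is at stake is precision in a pilot that, by Section I, may inform a larger study.

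**Working it through.** **Inputs.** From the documents: 15 participants, 4 sessions, 4 settings, significance level 0.05 (taken as two-sided, since sidedness is not stated). The sample size has no effect size, SD or power behind it, and Section V says that no variance data exist, so there is no plan figure to reproduce. Assumed: a linear drift of 0 to 1 within-person SD per session, and an effect of 1 within-person SD between two settings.

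**Step 1: position gaps if each participant draws one of the 24 orders independently.** The position of a setting has mean 2.5 and variance (4² − 1)/12 = 1.25. Two settings in the same person have covariance −1.25/3. Hence

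SD of the difference in mean position = √[(2 × 1.25 + 2 × 1.25/3)/15] = √(3.333/15) = 0.471 session.

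In 200,000 simulated lists, the gap for a given pair averages 0.38 session. The largest gap among the four settings has median 0.67 and 95th percentile 1.20. It exceeds 0.2 in 96% of lists and is at least 1 in 17%.

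**Step 2: the same with a 4×4 Williams square filled 4/4/4/3.** Sixteen people, four per sequence, would give every setting a position total of 4 × (1 + 2 + 3 + 4) = 40. Dropping one person removes 1, 2, 3 and 4 from the four totals, leaving 39, 38, 37 and 36. Divided by 15, the mean positions are 2.60, 2.53, 2.47 and 2.40, so the largest gap is 3/15 = 0.20. Exact equality is impossible with 15, because 15 × 2.5 = 37.5 is not a whole number.

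**Step 3: why drift costs power in an unadjusted paired test.** With independent orders and drift g (in SD per session), one person's difference between two settings has variance 2 + 3.333g². For a 1-SD effect the noncentrality is √15/√(2 + 3.333g²):

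- g = 0: 3.873/1.414 = 2.74
- g = 0.25: 3.873/1.486 = 2.61
- g = 0.5: 3.873/1.683 = 2.30
- g = 1: 3.873/2.309 = 1.68

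**Step 4: simulated power and type I error.** A paired t-test on one pair of settings stands in for the planned test, with 20,000 runs per case. The adjusted version regresses the paired difference on the difference in session position.

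| Drift per session | Independent, unadjusted: type I / power | Balanced, unadjusted: type I / power | Independent, adjusted: power | Balanced, adjusted: power |
|---|---|---|---|---|
| 0 | 5.1% / 72% | 4.8% / 73% | 68% | 72% |
| 0.25 SD | 5.1% / 68% | 4.0% / 68% | 68% | 71% |
| 0.5 SD | 5.2% / 57% | 2.4% / 57% | 68% | 71% |
| 1 SD | 5.1% / 34% | 0.4% / 27% | 68% | 71% |

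Adjusted type I error is close to 5% in all cases. Balance without adjustment makes the test conservative: the drift nearly cancels from the mean difference but still inflates the estimated error.

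**Step 5: what balance adds once session is in the model.** With participant, session and setting as factors, the variance of a setting contrast relative to the fully balanced bound of 2/15 is on average 8% higher with independent orders, against 0.4% higher with the 4/4/4/3 square. An 8% rise in variance is about 4% in standard error (√1.08 = 1.04). The worst contrast in a list is about 16% higher on average and 33% at the 95th percentile.

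**The case against.** The strongest reply has four parts.

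- **The order is randomised, so the comparison is valid.** This stands. Expected position is 2.5 for every setting, and average type I error is about 5% at every drift examined. A reader might infer that the settings comparison is biased; the documents and the arithmetic do not support that. What remains is chance imbalance in the single list that will be used, and a wider error term.
- **The protocol does not say that order is unrestricted.** This also stands. A reader might infer that balancing has been rejected, but the text is silent. The independent draw in Steps 1 and 4 is one scheme that would comply with the wording, not a description of what will be done. The missing session term does not depend on this inference.
- **No drift is shown, least of all in lactate.** The documents give no evidence of its size, and they contain partial safeguards: separate days, people who regard themselves as able to exercise regularly, warm-up sprints, constant seat settings and the 8-second pre-test efforts. None clearly removes learning of the 60-second test, but any stated amount of distortion in the primary endpoint would be assumption.
- **The square by itself changes little.** Correct. At 0.5 SD per session the unadjusted test has 57% power with or without it. The session term brings about 11 points (57% to 68%), and balance about 3 more. The Williams property of balancing which setting precedes which is a bonus; any Latin square balances position.

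**Conclusion.** The point holds as a cheap improvement, not as a flaw that invalidates the trial. The plan states no balancing of order and no session term, so any drift stays in the setting contrasts as avoidable noise.

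The size depends on a drift that the documents do not give. Without drift nothing is lost, and with independent orders the session term would cost about 4 points of power (72% to 68%). It breaks even at about 0.25 SD per session, gains about 11 points at 0.5 SD, and doubles power at 1 SD (34% to 68%). With a balanced list the cost at zero drift is about 1 point (73% to 72%), which is the main reason to adopt both together.

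These figures rest on a linear drift common to all participants, a paired t-test standing in for the Wilcoxon test, a 1-SD effect, and 15 completers.

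**What to change.** 1. **Main change, Section VIII.** Include session number (1 to 4) as a factor in the primary comparison between settings, for example in a mixed model with participant, session and setting. If the data are not normal, use a rank-transformed or session-adjusted response, because the Wilcoxon signed rank test cannot take a session factor. State that session number is the order actually attended, since Section V allows additional sessions.
2. **Supporting change, Section V.** Allocate participants from a pre-made list, in permuted blocks of four, to the four sequences of a position-balanced 4×4 square such as a Williams square. With 15 participants this gives 4/4/4/3.

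Adopt the two together: balance without the session term does not recover power and makes the unadjusted test conservative.

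The cost is a randomisation list, a modest change to the default analysis and a few degrees of freedom. No participants or sessions are added. Withdrawals would erode the balance: with three random dropouts the median largest gap is 0.33 session (95th percentile 0.67). The session term still adjusts for what remains.

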The **hypothesis** is that HVT, regardless of the oxygen concentration (i.e., FiO₂), will reduce the work of breathing and increase the lactate clearance rate during exercise and recovery intervals.

To test this hypothesis, the study will be conducted with the following specific aims:

Aim #1: Primary Outcome.

The primary endpoint is change in blood lactate from before the exercise test to recovery over a period of 30-60 minutes post-exercise.

Aim #2: Secondary Outcomes.

The secondary endpoints evaluate additional data that may be clinically meaningful. Data will include vital signs (SpO₂, heart rate [HR], respiratory rate [RR], blood pressure [BP]), and perceived level of exertion (BORG [score 0-10]), as measured during the exercise and recovery intervals. Work performance will be computed during test period only, including peak power output, mean power output over 30second intervals, and decrease in power.

Aim #3: Tertiary Outcomes.

The tertiary endpoints will evaluate the participant perceptions of the therapy impact during study procedures: (1) Level of Exertion at Exercise End, (2) Relief of Exertion Recovery End, (3) Comfort/Tolerance of Therapy at Study End [exercise and recovery], as measured on a 1-10 Likert scale.

1. Level of Exertion at Exercise End: "How tired do you feel?"
2. Relief of Exertion at Recovery End: "How fast do you feel you recovered?"
3. Comfort/Tolerance of Therapy at Therapy Segment End: "How comfortable was the therapy while you had it on during exercise? How comfortable was the therapy while you had it on during recovery?"

These **endpoints** will establish the effect of Vapotherm HVNI on lactate clearance, work of breathing, and perceived exertion during exercise and recovery intervals.

III. Participant Selection

Participants will be identified and recruited by study investigators. The study will take place in an appropriate educational forum (e.g., hospital, academic center, laboratory setting, etc.) where kinesiology testing can be accomplished. Initial contact will be made by study investigators, and volunteers may include any interested participants. Participants will be compensated for their time at a rate of approximately **\$50 per hour**.

Inclusion Criteria

1. Adults over 18 years old, in a general state of good health, of either sex
2. No known contraindication to performing a maximal exercise test, i.e., Wingate-type Anaerobic exercise test

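### Comfort during exercise is rated only at the end of recovery, so the rating is recalled and liable to be coloured by how the therapy felt during recovery

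*Combined protocol and SAP*

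**What the plan says.** Aim #3 (Section II) and the tertiary endpoint list (Section VII) define the comfort/tolerance item as two questions. The first is "How comfortable was the therapy while you had it on during exercise"; the second asks the same about recovery. Both are scored from 1 to 10.

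On timing, Section VI (Recovery Interval) says: "At end of recovery interval, participant perception of (1) Relief of Exertion at Recovery End, and (2) Comfort/Tolerance of Therapy will be recorded". Aim #3 labels the item once as taken at study end, for exercise and recovery together, and once as taken at the end of the therapy segment. Section VII uses the segment-end label, and Table 1 marks perception scores only under Study End.

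One perception question is placed earlier. Section VI (Wingate-type Exercise Test Procedures) says: "At end of exercise interval, participant will be asked their perception of their level of exertion". Comfort is not mentioned there.

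Section IV has the cannula worn, at the designated setting, through both exercise and recovery. It describes the trial as unblinded.

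**The concern.** The protocol chose to split comfort by phase, presumably because a setting could feel acceptable in one phase and not in the other. Collecting both scores together at the end works against that split. The participant has to look back past the whole recovery period to a short bout of maximal effort, and answers next to a question about recovery comfort and another about speed of recovery.

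If recovery comfort differs between 5 LPM and 25-30 LPM, part of that difference may pass into the exercise score. A comparison of settings on exercise comfort would then partly reflect recovery comfort. Section I says the pilot may inform a larger study, so a poorly timed item could be carried forward. Timing can only be corrected prospectively: no analysis recovers a rating that was not taken at the time.

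**Working it through.** The plan gives no figure for this item to reproduce. The check is of the schedule, with simple arithmetic on the delay.

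**Inputs**
- Length of the exercise test (Section VI): "the participant will pedal as rapidly as possible for 60 sec against the load determined for maximal power output", so 1 minute.
- Length of recovery (Section VI): "Recovery interval will take place after exercise period up to 1 hour, or until participant is fully recovered and lactate levels approach baseline".
- Primary endpoint window (Aim #1): "recovery over a period of 30-60 minutes post-exercise".
- Recovery lactate sampling (Section VI): "A minimum of 15 samples during the recovery interval will be performed". The Table 1 column is headed "Recovery Period q5min".

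**Delay from end of exercise to the exercise comfort rating**
- From the Aim #1 window and the 1-hour limit: about 30 to 60 minutes. This is 30/1 = 30 to 60/1 = 60 times the length of the test being rated.
- If the 15 samples were taken every 5 minutes: (15 − 1) × 5 = 70 minutes with the first sample at minute 0, or 15 × 5 = 75 minutes with the first at minute 5. That exceeds the 1-hour limit, a separate inconsistency to reconcile. For this point it shows only that a delay of about an hour is not an exaggeration.
- With the question moved to the end of exercise: about 0 minutes.

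**Do the passages agree on the late time?** For comfort, yes. Aim #3, Section VI, Table 1 and the endpoint list all put it at the end of the session, and none provides an earlier exercise comfort rating.

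**Does the design remove the problem?**
- Section V randomises the order of settings across sessions. Within every session exercise still precedes recovery, and both comfort questions come last.
- An equal delay at all settings would not cancel the effect, because what may be carried over is recovery comfort, which can itself differ by setting.
- The delay need not be equal. Recovery may stop early once the participant has recovered and lactate is near baseline, and the hypothesis is that the therapy speeds lactate clearance. If so, recall time would vary by setting.

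**Illustration only; both inputs are assumed.** Let a share w of the recalled exercise score reflect recovery comfort, and let two settings differ by D points in recovery and by 0 in exercise.
- Spurious exercise difference = w × D.
- Gap left between the recovery and exercise contrasts = (1 − w) × D.
- With D = 2 and w = 0.25: 0.25 × 2 = 0.5 spurious, 0.75 × 2 = 1.5 left.
- With D = 2 and w = 0.5: 0.5 × 2 = 1.0 spurious, 0.5 × 2 = 1.0 left.

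These results restate the assumptions. Their only use is to show that partial carry-over blurs the distinction between phases without removing it.

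**The case against.** The end-of-session timing is consistent across the protocol and the question is worded in the past tense, so it looks deliberate. The alternative is not free of bias either. A participant asked about cannula comfort straight after 60 seconds of all-out pedalling, alongside the exertion question and the other exercise-end measurements, may answer partly from exhaustion. The documents do not show which influence is larger. This stands as a real, small downside of the change. It does not defend the present timing, because exertion is already rated at that moment, so one more score is feasible, and the rating would then precede almost all of the recovery exposure.

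The contrast between a 1-minute exposure and an hour's delay is also less sharp than it looks. Section VI includes warm-up sprints and short load-finding intervals without saying whether the therapy runs during them, and recovery may end before the hour. That affects the ratio, not the order of events.

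A reader might go further and infer that the exercise score is in fact coloured by recovery, or that exercise and recovery comfort cannot be told apart. The documents support neither. Recall follows from the schedule; colouring is a reasonable inference that no passage demonstrates. The two questions are separate and phase-specific, so a participant can give two different scores.

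A reader might also take the study-end label to mean one rating after all four sessions. Section VI lists the comfort rating among the procedures for each test session, so that reading fails.

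Finally, the stakes are low. Section VIII does not name the tertiary endpoints and specifies no contrast of exercise with recovery comfort, and no decision rule uses the item. That is correct and sets the priority.

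**Conclusion.** The point holds as a low-priority improvement. The exercise comfort rating is recalled after roughly 30 to 60 minutes more on the same setting, and is liable to be coloured by recovery comfort. Exercise-specific differences between settings may be blurred as a result; the amount is unknown and cannot be derived from the documents. The conclusion rests on the stated schedule and on one assumption, that some of the recovery experience enters a rating given afterwards. It concerns one tertiary item. The lactate, Borg and power endpoints, the sample size and the error rate are unaffected.

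**What to change.** Ask the exercise comfort question at the end of exercise, together with the exertion question. Keep the recovery comfort question at the end of recovery.

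Amend four places so that they agree:
- **Aim #3:** give the two comfort questions separate times, replacing the study-end and segment-end labels.
- **Section VI:** add exercise comfort to the exercise-end questions, and limit the end-of-recovery comfort item to recovery.
- **Table 1:** perception scores are now marked only under Study End. Add an exercise-end entry, which would also cover the exertion rating that Section VI already places there.
- **Section VII tertiary endpoint list:** show the same two times.

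The cost is a wording change and one question moved on the case report form. The drawback to acknowledge is the extra question immediately after maximal effort, when exhaustion may influence the answer.

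### Section VIII's default route names no comparison among the four settings and no multiplicity adjustment, so the error rate on lactate is not held at 5%

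*Combined protocol and SAP*

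**What the plan says.** Section VI states: "The study will include four sessions, corresponding to four therapy settings being tested". They are two oxygen concentrations (21% and 100%) crossed with two flows (5 LPM and 25-30 LPM). The hypothesis in Section II concerns flow: HVT should lower the work of breathing and speed lactate clearance whatever the FiO2.

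The primary endpoint appears in two forms. Aim #1 in Section II describes a single change in blood lactate, from before exercise to recovery. Section VII lists "Change in lactate over (1) the exercise test interval, and (2) the recovery interval".

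Section VIII starts from an assumption of non-normal data. On that route, "a non-parametric test (e.g., Wilcoxon Signed Rank Sum test) will be performed with significance interval of 0.05 on all applicable variables". The other route reads: "If continuous variables present a normal distribution, between-trial comparisons will be performed using two-way (within-within; trial* post-exercise sampling times) repeated measures ANOVAs". Categorical variables go to Fisher's exact test. The section closes with: "Further analyses may be performed on the collected data based on ongoing analyses at time of study completion to identify additional relevant results".

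Section VIII does not say which settings are compared, which result decides the primary question, in what order tests are done, or whether any adjustment is made. Section V plans 15 participants with four sessions each and gives no effect size, SD or power. Sections I and IV describe the study as a pilot. Section II nevertheless presents the endpoints as establishing what the therapy does to lactate clearance.

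**The concern.** A signed-rank test needs two conditions. With four settings, the analyst must choose a pair or run several pairs, and the plan leaves that choice open. The choice between one lactate change and two is open as well. Each test would be run at 0.05, and nothing marks one of them as decisive.

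The 0.05 in Section VIII is therefore the error rate of one test, not of the conclusion on lactate. Section I says the results may provide the basis for a larger study and help choose its measures. A chance difference picked from several unadjusted tests in 15 people could steer that choice.

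**Working it through.** **Inputs from the documents**
- Settings: 4 (Section VI), so 4 × 3 / 2 = 6 pairs.
- Pairs that compare high with low flow: 4. Two are matched on FiO2 (setting 2 v 4, and 3 v 1); two also differ in FiO2 (2 v 1, and 3 v 4).
- Pairs that differ only in FiO2: 2 (1 v 4, and 2 v 3).
- Lactate endpoints: 1 (Aim #1) or 2 (Section VII).
- Participants: 15 (Section V). Level per test: 0.05 (Section VIII).

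**Assumptions**
- Tests are two-sided (not stated in the plan).
- There is no true effect, the four settings are exchangeable within a participant, and all 15 participants complete.
- Where there are two lactate endpoints, their correlation is 0, 0.5 or 0.8.

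**Step 1: the plan's own figure.** For n = 15 the exact two-sided signed-rank test at 0.05 rejects when the smaller rank sum is 25 or less. Its attained size is 0.0479. The nominal 5% therefore holds for one test of one pair. In one chosen direction the rate is half of that, 0.0479 / 2 = 2.4% (nominally 2.5%).

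**Step 2: several pairs.** If tests were independent, the chance of at least one false positive among k tests would be 1 − 0.95^k: 26.5% for k = 6 and 46.0% for k = 12. Pairs that share a setting are correlated, so these figures are too high. Simulation with exact critical values (60,000 trials, simulation error about 0.2 percentage points) gives:

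| Tests run on lactate | One endpoint | Two, r = 0.8 | Two, r = 0.5 | Two, r = 0 |
|---|---|---|---|---|
| All 6 pairs, either direction | 20.8% | 30.9% | 35.0% | 37.0% |
| 4 flow pairs, either direction | 16.0% | 24.4% | 27.9% | 29.1% |
| 4 flow pairs, favouring high flow | 8.0% | 12.5% | 14.4% | 15.3% |
| 2 FiO2-matched pairs, either direction | 9.4% | 14.6% | 16.8% | 17.6% |
| 2 FiO2-matched pairs, favouring high flow | 4.7% | 7.4% | 8.6% | 9.2% |

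A repeat with 200,000 trials gave 8.2% to 15.6% for the third row and 4.8% to 9.3% for the last, hence the rounded ranges of 8-16% and 5-9%.

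**Step 3: one prespecified contrast.** For each participant take (setting 2 + setting 3)/2 − (setting 1 + setting 4)/2 and apply one signed-rank test. With one lactate endpoint the simulated error is 4.9%. If both lactate changes stay primary and unadjusted, it is 7.6% (r = 0.8) to 9.4% (r = 0), so the endpoint has to be settled too.

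**Step 4: other ways to hold the error (one endpoint).** A Friedman test across the four settings has size 4.5%. Requiring it to be significant before any pair counts gives 4.2%. Bonferroni over six pairs (0.05 / 6 = 0.0083 each) gives 3.5%. With no true effect, Holm's first step is that same threshold, so it also gives 3.5%.

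**The case against.** Four points on the other side deserve weight.

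- **The plan does contain a four-setting test.** The signed-rank test is only an example, and normally distributed data go to a repeated-measures ANOVA across settings. A reader might infer that every variable gets a two-condition test and that no overall test exists; the text does not support that. However, non-normality is the plan's starting assumption, and only the ANOVA route has an overall test. The ANOVA is also limited to post-exercise sampling times, so it does not cover the change over exercise. It names neither the decisive term nor any follow-up procedure.
- **The plan never says that six pairs will be tested.** This is correct. The six-pair figures show what the wording allows, not what it prescribes. The defect is that the comparison is not specified.
- **The 21-37% is not the chance of wrongly concluding that HVT works.** A reader might take it so. It includes the two pairs that differ only in FiO2, and results against high flow. If success required both FiO2-matched pairs to favour high flow, the chance would be about 0.1% or less. But the plan states no such rule.
- **This is a pilot with ranked endpoints and no power claim.** That lessens the consequence. It does not remove it, because Section VIII sets a significance threshold without calling any test exploratory.

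Two further inferences are not supported. Counting intervals separately, there are about 19 variables (2 lactate + 8 vitals + 2 Borg + 3 work + 4 perception), but that count plays no part in the lactate figures. Nor does the plan say that lactate will be tested separately at each recovery sample, so no error rate is claimed for that.

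**Conclusion.** The point holds for the default, non-normal route. Followed as written, it does not keep the error on lactate at 5%, because the comparison is open, the number of primary lactate changes is inconsistent, and nothing is adjusted.

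The size depends on what is counted. A false high-flow benefit is roughly two to six times as likely as the nominal 2.5% (4.7 / 2.5 = 1.9; 15.3 / 2.5 = 6.1). The larger 21-37% applies only to any lactate difference in either direction across all six pairs. Its upper end needs two uncorrelated lactate endpoints. All figures rest on the assumptions listed with the calculation. They do not show that a positive result would be false, only that the stated level would not describe its reliability.

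**What to change.** 1. Name one primary lactate endpoint, with its start and end times, and make Aim #1 and Section VII agree.
2. Make the primary test one prespecified flow contrast at 0.05, two-sided: each participant's mean over the two high-flow settings minus the mean over the two 5 LPM settings, tested by signed-rank. This addresses the hypothesis across both FiO2 levels, which no single pair does. State how participants without all four sessions are handled.
3. For other lactate comparisons, use an overall four-setting test (Friedman, or the ANOVA setting term if data are normal), then Holm-adjusted pairs. Present them as support for the primary result, not as alternatives to it.
4. Label secondary, tertiary and data-driven analyses as exploratory, reported as estimates with 95% confidence intervals.
5. Soften Section II's claim that the endpoints settle the therapy's effect, to fit a pilot.

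**Cost.** The change is to wording only. Adjusted pairs lose power: with 15 participants and normally distributed differences, about 80% power needs a difference of roughly 1.1 SD of the paired difference at Holm's first step, against 0.8 SD unadjusted. The primary contrast loses none. With equal variances σ² and equal correlation ρ between settings, a single pair difference has variance 2σ²(1 − ρ) and the contrast has σ²(1 − ρ). The contrast is therefore the more precise of the two, and gains power if the flow effect is similar at both FiO2 levels.
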